Original	March 27, 2020	N/A
V2.0	April 13, 2020	Revised study title and added 3 months of longitudinal follow-up
V3.0	December 7, 2020	Revised duration of follow-up from 3 months to 12 months, removed questions on social distancing, and added questions on mental health conditions, healthcare encounters, and vaccines.
V4.0	March 9, 2021	Revised inclusion criteria to include vaccinated adults as well as participants from the UK; added questions about post-vaccination symptoms and health care encounters.

List of Abbreviations

COVID-19	coronavirus disease 2019
FDA	U.S. Food and Drug Administration
GDPR	General Data Protection Regulation
GPP	good pharmacoepidemiology practices
HIPAA	Health Insurance Portability and Accountability Act of 1996
ICF	informed consent form
ICH	International Council for Harmonisation of Technical Requirements for Pharmaceuticals for Human Use
IEC	independent ethics committee
IRB	institutional review board
ISPE	International Society for Pharmacoepidemiology
NSAID	nonsteroidal anti-inflammatory drugs

Study Synopsis

Full Study Title: Registry to study factors that may impact COVID-19 occurrence and severity

Background & Rationale: The 2019 coronavirus disease (COVID-19) has presented major challenges to countries around the world. Currently there is little information about (1) symptom presentation, severity, and duration especially for cases that do not require hospitalization, (2) understanding which prescription medications, if any, influence risk, including various hypertension and anti-diabetic medications, (3) whether vitamin and mineral supplements, alone or in combination with established medications offer any degree of protection, and (4) what medical management is most effective at reducing the high toll of this infection.

Initial research suggests a wide range of potential symptoms including those that would be expected with a respiratory virus (e.g., fever, cough) as well as gastrointestinal issues, dizziness, inability to concentrate, and effects on the sense of smell and taste. Additionally, there are a wide range of treatments, both prescribed and over-the-counter, that are being used to manage symptoms. Systematic data collection and analytics will contribute empirical information about benefits and risks that could have immediate public health impact. This registry will enroll participants in an observational, direct-to-participant longitudinal study to assess disease risk, progression, treatments, and vaccines.

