2. OBJECTIVES

The objectives of this study are to:

1. Identify factors that may impact the occurrence or severity of COVID-19 infections including examining the role of underlying health conditions, prescription and over-the-counter medications, vitamins and supplements.
2. Assess post-vaccine symptoms and COVID-19 infection among participants reporting a COVID-19 vaccination

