3.3.1 Baseline/Enrollment

The following data are planned to be collected at baseline for all enrolled participants:

- Demographics

- geography (zip code/ postcode)
 - age (date of birth)
 - gender
 - race/racial designation
 - ethnicity
 - education
- Medical History and Other Risk Factors
 - weight
 - height
 - baseline medical history including:
 - comorbidities that are thought to be potential risk factors including cardiovascular disease, lung disease, diabetes, kidney, blood disorders, and auto-immune conditions
 - history of depression, anxiety, and insomnia
 - prescription medications
 - frequency of use of certain medications of interest, including daily aspirin, Pepcid (famotidine), Tagamet HB (cimetidine), and antihistamine (cetirizine, loratadine)
 - use of supplements (vitamin D, zinc, other vitamins/minerals, herbals)
 - current smoking status
 - history of organ transplant
 - current treatment for cancer
 - pregnant
 - vaccinations, including childhood vaccinations (e.g. MMR) and seasonal flu
 - occupation, including healthcare worker or other job with heightened risk of exposure (e.g., grocery, daycare, mail/delivery)

- COVID-19
- type of test, test results and date of test, if any
- presence and severity (4-point scale) of symptoms including fever, cough, fatigue, dizziness, eye pain, blurry vision, shortness of breath, persistent pain or pressure in the chest, heart palpitations, new onset of confusion, inability to arouse, aches and pains, muscle twitching, rash, nasal congestion, runny nose,

sore throat, decreased sense of taste, decreased appetite, decreased sense of smell, diarrhea, vomiting, nausea, depression, anxiety, insomnia, other

- healthcare encounters, including type (telemedicine, office visit, emergency department, hospitalization), date, and whether the encounter was related to COVID-19
 - if hospitalized, duration of hospitalization
- household member has COVID-19 or flu-like symptoms
- receipt of COVID-19 vaccination, either as part of a clinical trial or standard of care once authorized by FDA or Medicines and Healthcare products Regulatory Agency (MHRA), along with date, manufacturer, and lot number if known, and whether it was the first shot or a booster shot.
 - among vaccinated:
 - symptoms following the vaccination including pain at injection site, swollen lymph nodes, fever, fatigue, headache, joint or muscle pain, nausea or vomiting, severe allergic reaction

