 - impact symptoms had on ability to take care of yourself and ability to work
 - healthcare encounters, including hospitalization, following the vaccination
- medications including prescriptions (antimalarials, antivirals, antibiotics, biologics, corticosteroids, monoclonal antibody), over-the-counter (acetaminophen, nonsteroidal anti-inflammatory drugs [NSAIDs]),
 - for treatments the participant reports taking, timing of treatment relative to symptom onset
- participation in clinical trials or receipt of experimental treatments

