3.3.2 Follow-up

The following data are planned to be collected for all enrolled participants once a week during Month 1, twice a month during Months 2 through 12. Participants reporting a COVID-19 vaccine (first or second dose/booster) will be followed weekly for 4 weeks after their COVID-19 vaccine to capture symptoms, medical encounters and a booster, if applicable. Participants will be asked during follow-up to report any changes in their medical history (e.g., new comorbidities, prescription medications, pregnant) to reduce participant burden and allow for capture of updated medical history that may influence risk factors and disease progression.

- COVID-19
 - type of test, test results and date of test, if any

- presence and severity (4-point scale) of symptoms including fever, cough, fatigue, dizziness, eye pain, blurry vision, shortness of breath, persistent pain or pressure in the chest, heart palpitations, new onset of confusion, inability to arouse, aches and pains, muscle twitching, rash, nasal congestion, runny nose, sore throat, decreased sense of taste, decreased appetite, decreased sense of smell, diarrhea, vomiting, nausea, depression, anxiety, insomnia, other
- healthcare encounters, including type (telemedicine, office visit, emergency department, hospitalization), date, and whether the encounter was related to COVID-19
 - if hospitalized, duration of hospitalization
- household member has COVID-19 or flu-like symptoms
- receipt of COVID-19 vaccination, either as part of a clinical trial or standard of care once authorized by FDA or Medicines and Healthcare products Regulatory Agency (MHRA), along with date, manufacturer, and lot number if known
 - among vaccinated:
 - symptoms following the vaccination including pain at injection site, swollen lymph nodes, fever, fatigue, headache, joint or muscle pain, nausea or vomiting, severe allergic reaction
 - impact symptoms had on ability to take care of yourself and ability to work
 - healthcare encounters, including hospitalization, following the vaccination
- medications including prescriptions (antimalarials, antivirals, antibiotics, biologics, corticosteroids), over-the-counter (acetaminophen, NSAIDs),
 - for treatments the participant reports taking, timing of treatment relative to symptom onset
- participation in clinical trials or receipt of experimental treatments
- Medical History and Other Risk Factors (if participant reports a change in medical history since last survey)

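### No symptom-onset date, treatment start date or treatment setting is listed, so drugs first given in hospital cannot be reliably separated from earlier use when both are reported at baseline or within one survey interval

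*Protocol*

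**What the plan says.** For COVID-19 treatments, section 3.3.1 asks about "medications including prescriptions (antimalarials, antivirals, antibiotics, biologics, corticosteroids, monoclonal antibody" and over-the-counter drugs. The only timing item is "for treatments the participant reports taking, timing of treatment relative to symptom onset". Section 3.3.2 repeats that item at follow-up.

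Hospital care is recorded differently: "healthcare encounters, including type (telemedicine, office visit, emergency department, hospitalization), date, and whether the encounter was related to COVID-19", with the sub-item "if hospitalized, duration of hospitalization". Symptoms are listed as "presence and severity (4-point scale) of symptoms including fever, cough, fatigue" and many others, with no date of onset in either section.

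The synopsis rationale names as an open question "what medical management is most effective at reducing the high toll of this infection". Objective 1 in section 2 is to "Identify factors that may impact the occurrence or severity of COVID-19 infections including examining the role of underlying health conditions, prescription and over-the-counter medications", as well as vitamins and supplements.

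Under section 3.3.2, follow-up data are collected "once a week during Month 1, twice a month during Months 2 through 12". The synopsis instead says monthly for Months 2 to 12. Section 4.2.1 commits to descriptive analyses and leaves in-depth work to later objective-specific plans.

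**The concern.** Hospitalization is one of the few concrete markers of severity that the registry collects. Several of the listed drug classes could be started either before an admission or because of it. To study whether a drug influences severity, one must know which came first.

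The listed items do not reliably give that order. A participant who was admitted, first received a corticosteroid on the ward and enrolled after discharge reports the drug, its timing from onset, and the admission date. A participant who took the same drug at home and was admitted later reports the same kinds of facts. If both count as exposed, treatment given because of severe disease may look like a factor leading to it. An analysis plan can define exposure as use before admission, but it cannot apply that definition where the order was never collected.

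**Working it through.** The protocol states no figure on this point, and no sample size or power calculation, so there is nothing to reproduce. The check has three steps.

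**1. What the listed items can order.** Timing recorded in sections 3.3.1 and 3.3.2:

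| Item | Timing listed |
|---|---|
| COVID-19 test | date |
| Healthcare encounter, including hospitalization | date; length of stay if hospitalized |
| COVID-19 vaccination | date |
| Symptoms | none; presence and severity only |
| COVID-19 treatment | relative to symptom onset |

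Let S be symptom onset, T treatment start and A admission. The question is the sign of T − A. The treatment item gives R = T − S, and the encounter item gives A. Then T − A = R − (A − S), which needs S. S is not listed. T itself and the place of first use are not listed either.

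**2. What repeated surveys recover.** A drug reported in a survey completed before a dated admission was used before that admission. For a drug started g days before admission, with survey interval L and the survey phase taken as uniform, the chance that a survey falls between the two is min(1, g/L). The gaps are assumed, and every survey is taken as completed.

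| Interval L | g = 3 days | g = 5 days |
|---|---|---|
| 7 days (Month 1) | 3/7 = 0.43 | 5/7 = 0.71 |
| 15 days (twice a month) | 3/15 = 0.20 | 5/15 = 0.33 |
| 30 days (monthly, as in the synopsis) | 3/30 = 0.10 | 5/30 = 0.17 |

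For illness, treatment and admission that all precede enrollment and are reported together at baseline, the surveys give no ordering. Such people are eligible, since having COVID-19 is one of the listed routes into the study.

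**3. How large the distortion could be.** Take a drug with no effect. Let p be use before any admission, equal in hospitalized and non-hospitalized cases, and q the share of admitted non-users who are first given it in hospital. Recorded use among the hospitalized is e = p + (1 − p)q. The apparent odds ratio is [e/(1 − e)] / [p/(1 − p)]. All p and q are assumptions; the protocol gives none.

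| p | q | e | Apparent odds ratio |
|---|---|---|---|
| 0.05 | 0.10 | 0.145 | 3.2 |
| 0.05 | 0.20 | 0.240 | 6.0 |
| 0.05 | 0.50 | 0.525 | 21 |
| 0.20 | 0.20 | 0.360 | 2.25 |
| 0.40 | 0.05 | 0.430 | 1.13 |

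For the third row: 0.05 + 0.95 × 0.50 = 0.525, and (0.525/0.475)/(0.05/0.95) = 21. If only pre-admission use counts, the odds ratio is 1.0 by construction. The table treats every in-hospital start as misclassified, so it is an upper bound for given p and q where surveys resolve some of the order.

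**The case against.** The strongest reply has four parts.

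- **Two time scales are not in themselves a fault.** A treatment timed from onset can be compared with a dated admission once onset is dated. This is right, and it is why the point rests on the missing link and not on the use of different clocks. The protocol lists topics, not question wording. The survey instrument is not shown, and it may hold an onset date or ask timing in days. But the protocol names a date for tests, encounters and vaccinations and none for onset or treatment.
- **Order can often be recovered in follow-up.** A reader might infer that in-hospital and earlier use can never be separated. The documents do not support that: surveys recur, section 3.3 lets participants enter data at any time, and an analysis can take exposure at one survey and admissions after it. What remains is illness reported at baseline and events within one survey interval. Completion of every survey is also optimistic, since section 4.2.2 expects losses particularly among the very sick.
- **No causal analysis is fixed.** A reader might infer that hospital drugs will be reported as causes of severe disease. Section 4.2.1 fixes no such model, so the most that can be said is that they may appear associated with it. The definition of exposure properly belongs to the later plans.
- **The onset-timing item is useful.** A reader might also infer that it creates immortal time for outcomes counted from onset. It does the opposite: treatment time from onset is what a time-varying exposure analysis needs. The item should therefore be kept.

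It is also fair that severity is measured by repeated symptom scores as well as hospitalization, and that the problem is smaller for over-the-counter drugs and long-term medicines already in the medical history.

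**Conclusion.** The point holds within limits. As listed, the data items do not link treatment to admission. In-hospital starts therefore cannot be reliably separated from pre-admission use for illness reported at baseline, or when treatment and admission fall within one survey interval. Elsewhere in follow-up, a report made before a dated admission settles the order.

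The possible bias runs from negligible to large: an odds ratio of about 1.1 for a drug widely used before admission and seldom started in hospital, up to 21 for one started mainly in hospital. This range rests on assumed use, a truly null drug and an analysis that counts all recorded use as exposure. The conclusion about ordering rests only on the item lists, and would fall away if the instrument already records onset date, treatment start date or setting. The change is worth making because it concerns data that no later plan could supply.

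**What to change.** In sections 3.3.1 and 3.3.2, keep the existing onset-timing item and add:

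- the date of symptom onset, or best estimate;
- for each reported treatment, either the start date (or best estimate) or one tick item for whether it was first taken before, during or after an emergency department visit or hospital stay, with a not-applicable option.

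The onset-timing item should not be replaced by a start date alone, because it is the only listed link between treatment and onset. If the instrument already holds these fields, it is enough to list them in the protocol. How exposure is defined can be left to the objective-specific analytic plans.

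The cost is a few web-form fields, slightly more participant burden and some recall error in dates, with no extra staff or participants. Section 5.3 already foresees refining the instrument. Participants who have already reported could be asked once for the added items, with more recall error the longer ago the illness was.

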3.2.1 Inclusion Criteria

The following criteria must be met in order to be enrolled in the study:

- Adult (18 years or older)
- Currently living in the US or UK
- Have COVID-19 or COVID-19 like symptoms
- Received a COVID-19 vaccine
- Potential exposure to COVID-19

- Have regular access to a computer, smartphone or tablet and sufficient internet to support registry demands (note: this registry is designed to operate well even in regions with low bandwidth)
- Willing and able to provide informed consent
- Willing and able to follow the procedures of the study

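### For people already ill at enrolment, the listed items cannot tell supplement or regular-medicine use before illness from use begun because of it

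*Protocol*

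**What the plan says.** **Objective.** Protocol section 2 includes "examining the role of underlying health conditions, prescription and over-the-counter medications, vitamins and supplements" among the tasks of Objective 1, for both the occurrence and the severity of infection. The synopsis rationale also asks whether vitamin and mineral supplements protect.

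**Who enters.** Section 3.2.1 lists several routes. One is "Have COVID-19 or COVID-19 like symptoms"; another is "Potential exposure to COVID-19"; vaccination is a third. Some participants are therefore already ill when they answer the baseline survey and others are not. The protocol gives no expected mix.

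**What is recorded.** In section 3.3.1, under medical history and other risk factors, the items are "use of supplements (vitamin D, zinc, other vitamins/minerals, herbals", "frequency of use of certain medications of interest, including daily aspirin, Pepcid (famotidine), Tagamet HB (cimetidine" with two antihistamines, and prescription medications without further detail. None carries a start date, a look-back window or a reference to onset. The item "for treatments the participant reports taking, timing of treatment relative to symptom onset" appears once in that section, as a sub-item of the COVID-19 medications. That list runs from antimalarials to "over-the-counter (acetaminophen, nonsteroidal anti-inflammatory drugs [NSAIDs" and names no supplement. Section 3.3.2 repeats the same structure, with the medical-history items updated only when a participant reports a change since the last survey.

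**The concern.** A person who has taken zinc for years and a person who began it on the second day of fever give the same baseline answer. If both enrol while ill, the record cannot say which use came first. Illness can then cause the exposure rather than the reverse. A product with no effect may look harmful for occurrence, and a protective one may look neutral or harmful. For severity the error can run in either direction, depending on whether mild or severe cases are more likely to start a product.

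The protocol leaves in-depth analyses to later plans written for each objective. That does not settle this point, because an analysis plan cannot recover an order of events that was not collected. The limitations in section 4.2.2 cover self-selection, misreporting and loss to follow-up, but not reverse causation.

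**Working it through.** The protocol states no figure on this point, so there is nothing to reproduce. The check has two parts.

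**1. Which participants are affected**

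- *Ill at enrolment.* Baseline use is recorded after onset, with no start date. Prior and illness-prompted use cannot be separated. Changes reported at later surveys do fall after onset, so the ambiguity lies in the baseline answer.
- *Ill after enrolment.* The baseline answer precedes illness, and severity is then scored during follow-up. New use is placed within one survey interval: weekly in Month 1, then twice a month by sections 3.1, 3.3 and 3.3.2 (the synopsis says monthly). Only a product started in the same interval as the illness remains unordered.

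**2. How large the distortion could be**

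Every input here is an assumption; none comes from the protocol.

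- p = 0.20, true prior use in ill and not-ill people alike, so the true odds ratio (OR) is 1.
- s = share of ill non-users who start after onset: 0.05, 0.15 or 0.30.
- All cases are ill at enrolment, and no comparator starts.

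Recorded use among the ill is p₁ = p + (1 − p)s. The apparent OR is [p₁/(1 − p₁)] / [p/(1 − p)], with p/(1 − p) = 0.20/0.80 = 0.25.

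| s | p₁ | odds | apparent OR |
|---|---|---|---|
| 0.05 | 0.20 + 0.80 × 0.05 = 0.24 | 0.24/0.76 = 0.316 | 1.26 |
| 0.15 | 0.20 + 0.80 × 0.15 = 0.32 | 0.32/0.68 = 0.471 | 1.88 |
| 0.30 | 0.20 + 0.80 × 0.30 = 0.44 | 0.44/0.56 = 0.786 | 3.14 |

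Relaxing two of these assumptions for the middle row:

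- *Comparators also start.* If 10% of comparator non-users begin the product, their recorded use is 0.20 + 0.80 × 0.10 = 0.28. The OR is (0.32/0.68)/(0.28/0.72) = 1.21.
- *Only half the cases are ill at enrolment.* Recorded use among cases is 0.20 + 0.5 × 0.80 × 0.15 = 0.26. The OR is (0.26/0.74)/0.25 = 1.41.

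*A truly protective product.* Take 30% prior use among comparators and a true OR of 0.70. Prior odds in cases are 0.70 × 0.30/0.70 = 0.30, so prior use is 0.30/1.30 = 0.231. With 10% starting, recorded use is 0.231 + 0.769 × 0.10 = 0.308 and the apparent OR is 1.04. With 20% starting it is 1.46.

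*Severity.* Take 30% prior use and no true effect. If 5% of mild and 20% of severe non-users start, recorded use is 0.30 + 0.70 × 0.05 = 0.335 in mild cases and 0.30 + 0.70 × 0.20 = 0.44 in severe cases. The apparent OR is (0.44/0.56)/(0.335/0.665) = 1.56. If the two starting rates are swapped, it is 1/1.56 = 0.64.

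If starts after onset can be identified and set aside, s = 0 in the exposure variable and each of these distortions due to starting among the ill disappears.

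**The case against.** The strongest reply is that the protocol does not commit the error. A reader might infer from the filing under medical history and risk factors that all baseline use will be counted as prior exposure, so that reverse causation is built into Objective 1. The document does not support that. No section defines exposure, the detailed analyses are deferred, and section 4.2.2 expects systematic error from misreporting and incomplete follow-up to be handled analytically. This part of the objection stands.

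A reader might also infer that restricting to people not yet ill would help only the occurrence analysis. That is wrong too. People who fall ill after enrolment have a baseline record that precedes both the illness and its severity. The restriction does, however, leave out those already ill at entry, for whom the order remains unknown.

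Third, sections 3.3.1 and 3.3.2 list planned topics; the questionnaire is not shown, and section 5.3 allows it to be refined. No onset date is listed as its own item either, although the treatment-timing item depends on one. The timing item could also pick up a supplement, or one of the regular medicines, that the participant reports as a COVID-19 treatment. So it cannot be said that the survey never asks. It can be said that the protocol lists timing for one group of products and not for the other, and that the supplements named in Objective 1 are in the second group.

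Finally, the odds ratios rest on assumed rates and on a scenario that favours a large effect. That is correct, and the relaxed cases above show how much they shrink.

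**Conclusion.** The point holds for participants who are symptomatic or test-positive at enrolment. For them, the listed items on supplements, medicines of interest and prescription medicines cannot separate use before illness from use prompted by it, and reverse causation cannot be ruled out for occurrence or severity. It largely does not apply to participants who become ill after enrolment.

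The size is unknown. In the main illustration the apparent OR for a product with no effect is 1.26 to 3.14; the middle value of 1.88 falls to 1.41 or 1.21 when one assumption is relaxed. These figures show that modest starting rates could matter. They are not estimates for this registry, whose share of already-ill entrants is not given. The gap is worth closing because it affects a stated objective, is cheap to close, and uses a kind of question the protocol already plans for treatments.

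**What to change.** - **Section 3.3.1:** for each supplement and regular medicine reported by a participant who has symptoms or a positive test, add one question: did use begin before or after onset (or the positive test)?
- **Section 3.3.2:** ask the same question only when new use and new illness are reported in the same survey interval.
- **Analysis plan for Objective 1:** for already-ill entrants, count only use begun before onset as exposure, and report later use separately. As a sensitivity analysis, restrict occurrence and severity to illness arising after enrolment. This also helps because the new question does not date use among comparators, whereas in the restricted set everyone's exposure is taken at baseline.
- **Section 4.2.2:** name reverse causation among the limitations.

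The cost is a slightly longer survey for those already ill and some recall error about start times. Answers already collected without the question stay ambiguous, so the restricted analysis is the only protection for those records.
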